6.1 Ontological and epistemological positioning

The process evaluation methodology will be underpinned by a Critical Realist Ontology. Critical Realism posits that an independent reality exists, but such a reality is context-dependent, the result of interacting mechanisms, and that different perspectives on or experiences of this reality exist. The quantitative component will be underpinned by a Post-Positivist Epistemology which aims to ascertain objective knowledge whilst acknowledging that research methods and interpretations are inherently limited by the researchers' values and culture. The qualitative component will be underpinned by Contextualism, which seeks to ascertain a situated knowledge, understood only by exploring the multiple and subjective perceptions of reality and how these are shaped by human values and context. 54,56

6.2 Quantitative component

The quantitative component will aim to address the following research question:

What works, how does it work, and for whom?

We will report descriptive statistics on key intervention uptake and engagement metrics, such as the number and proportion of participants completing at least the first session, the average

number of sessions completed, and the average number and duration of coach calls completed. In addition to the main statistical analyses described in the above analysis plan, we will examine mediators and moderators of intervention effects informed by our SWiM programme theory (Appendix A). The following variables will be analysed for potential mediating or moderating effects (depending on the programme theory) on the primary outcome: psychological flexibility, depression, anxiety, stress, impulsivity, pain, sleep, diet, physical activity, uncontrolled eating, emotional eating, and number of coach calls attended. We will explore whether intervention effects differ by sociodemographic subgroups by exploring moderating effects of PROGRESS-PLUS criteria, as outlined in section 5.2.

6.3 Qualitative component

The qualitative component will aim to address the following research questions:

How is SWiM perceived, experienced and applied over time across individual contexts?

Why do components of SWiM work or not work, and under what contexts?

What additional unintended outcomes (positive/negative) are experienced?

Qualitative data will be collected via longitudinal and cross-sectional semi-structured interviews via zoom or telephone at 6 and 18-months. Stratified, purposive sampling will be employed to ensure; maximum heterogeneity in engagement and 6m weight change and representation across individual characteristics and demographic groups to understand patient journeys. 6 months is chosen to capture intervention completion and 18-months for long-term outcomes. The sample size will be determined by a process of information power, although it is estimated that a sample of 15 (three per each of the five referring weight loss programmes) will be necessary to achieve the desired diversity. 57,58 Co-produced interview schedules will explore how the programme was perceived, experienced and applied across different groups, unanticipated impacts, and long-term sustainability. The interview schedule will be informed by the Client Change Interview. Interview data will be analysed using reflexive thematic analysis⁵⁴ with support from a (trained) patient panel member. An abductive approach to coding and theme development will be employed, informed by the revised SWiM programme theory, the Theoretical Framework of Acceptability,⁵⁹ and Capability - Opportunity - Motivation - Behaviour Model,⁶⁰ whilst also seeking to generate new explanations and extend the programme theory. Recordings will be transcribed by an experienced external agency and checked for accuracy by the research team. Verbatim transcripts will be coded using NVivo software and/or paper-based coding. Methods to enhance rigour will include the use of a reflective diary throughout data collection and analysis, the involvement of a public panel member, and the progression of coding iterations will be documented to track the evolution of codes and prospective themes. Reflexive discussions will be held amongst the research team to clarify and deepen analytic insights and enhance the quality of the developing analysis. 54,61

Qualitative and quantitative data will be analysed separately, then integrated using a joint tabular display. 62,63

7. Delivery Evaluation

7.1 Fidelity in programme delivery

A fidelity assessment will be conducted to evaluate whether SWiM is delivered as intended by the SWiM coaches. Underpinned by Ontological Realism and Epistemology Post-Positivism, this assessment will address the following research question:

To what extent is SWiM delivered as intended?

Data will be collected via observations of session recordings. At a minimum, we intend to recruit six coaches for programme delivery and observe a sample of two complete courses (one course \approx four coach calls) across all six coaches, equating to twelve samples (total N=48 coach calls). If additional coaches are recruited, further observations will be governed by a process of information power. A checklist of core SWiM session parameters (e.g., duration) and content will be developed by the programme development team. The checklist will be assessed for interrater reliability using a sample of session recordings, observed and coded by two researchers individually and in duplicate. This will inform checklist refinements before the full-scale fidelity assessment.

All session recordings will be observed and coded against the refined checklist individually and in duplicate by two researchers. Inter-rater reliability will be analysed and reported and all discrepancies between the two coders will be resolved through discussion. Data will be analysed descriptively to report the degree of fidelity.

7.2 Experiences of health coach delivery

To understand the contextual factors influencing the delivery of SWiM, a qualitative study will be conducted to explore health coaches' perceptions and experiences of delivering SWiM, including barriers and facilitators to delivery. This will be underpinned by a Critical Realist Ontology and Contextualist Epistemology, aiming to address the following research questions:

How is the delivery of SWiM perceived and experienced by the health coaches?

What are the barriers and facilitators to delivering SWiM with fidelity to the programme theory and coach manual?

8. DATA MANAGEMENT

The MRC Epidemiology Unit has an over-arching data management policy (DMP) that encompasses the standards and processes applied to all research and operational activities in the Unit. The PIs will ensure that all data generated, stored and shared from this trial will be handled in compliance with the DMP and the General Data Protection Regulations. The data controller will be the University of Cambridge. The legal basis for holding and processing the data as outlined in the protocol is to enable the team to conduct health research in the public interest.

8.1 Data Collection tools and source documentation

The MRC Epidemiology Unit uses a Secure Research Domain (SRD), which is a computer network that has been designed to securely store PID, and which is considered a safe haven for storing

PID by the University of Cambridge. All Participant Identifiable Data (PID) are stored only within the SRD. The SRD has security features and policies to ensure only a minimum number of named, qualified staff have access to this sensitive information. All SRD users have a contract with the Unit and are trained in data security. In addition, all access to the SRD involves 2-Factor Authentication (2-FA) and has a number of security features in place to protect this data.

We will export PID from the SRD under the following circumstances necessary to running the study:

- Transfer of name and email between us and the referring service provider/commissioner to establish contact with participants/check they are not contacted more than necessary. Data transfer via NHS email, sFTP or provider's secure website
- Transfer of participant name, address, and height and weight to the cellular-scales provider for the purpose of setting up and shipping the cellular-scales. Data transfer via developer API secured by HTTPS and OAuth2.0.
- Transfer of mobile phone number and name to the SMS provider for sending of SMSs between the study team and the participant. Data transfer via sFTP or provider's secure website.
- Transfer of name and email address to Cauldron for set up of participant accounts on the study intervention website. Data transfer via sFTP or provider's secure website.
- Name and address labels for posting finger-prick home kits.
- Transfer of name, date of birth, and NHS number to national registries for linkage of study data to registry data. Data transfer via sFTP or provider's secure website.

All other participant data used in SWiM 2.0 monitoring and analysis will be pseudonymised. This involves assigning a unique study ID to each participant and then removing all data that could allow a participant to be directly identified. The anonymous study ID will also be used for data collection using the REDCap surveys, weight measurements from the cellulare-scales and for the HbA1c result.

The scientists, study team and other members of staff who deal with the participants' data, but who do not need to be in contact with the participant, will only have access to the pseudonymised data, thus allowing them to carry out analysis and other data tasks without compromising the privacy of study participants.

Participation will be under full informed e-consent, including for the storage and use of data collected. At any point, participants can choose to opt out of any aspect of data collection or processing. As stated on the information sheet, any data collected up until the point of withdrawal will continue to be held by the study team.

8.1.1 Source data collected at home

Questionnaire data collected remotely via REDCap forms will be linked to the participant using the study ID only (i.e. no identifiable data).

Because the initial expression of interest form is a publicly-available link, we will take extra steps to filter out bots and multiple registrations. We will use a REDCap Captcha module to provide a score for the likelihood that the form has been filled out by a human rather than a bot, add hidden questions to filter out bots, and confirm provided phone numbers by sending an SMS message expecting a reply. We will also filter out entries with duplicate addresses, emails, or phone numbers.

8.1.2 Source data collected via cellular-scales

The cellular-scales will send participants' weight measurements over cellular data to Withings' GDPR compliant servers in the EU and then retrieved using the Withings developer API directly to the Epi Unit's secure research data server. Data transfers are secured using HTTPS and OAuth2.0 authentication. Weight measures will be linked to the participant using the study ID only (i.e. no identifiable data).

8.1.3 Source data collected via HbA1c test

The blood results collected via finger prick will be sent from The Doctors Laboratory directly to the study team in batches. Blood results will be linked to the participant using the study ID only (i.e. no identifiable data).

8.2 Data handling and record keeping

Where possible, on study specific documents and in all places where a participant needs to be referenced, the participant will be referred to by their study ID number, not by name. However, for some documents e.g. informed consent, the participant's name will be present.

All participant level data will be entered and stored on the Unit's SRD to which access is restricted via unique username and password as well as 2-FA. Participant data will be link anonymised (pseudonymised) at the point of data release. Direct quotations about participation in the study will only be used with explicit written permission from the participant unless the quote is anonymised. All data handling, processing, transfer and storage procedures comply with our obligations under the latest Data Protection Act, which incorporates GDPR.

The study database will also be used to record study data, including randomisation group, eligibility criteria met and completion of online assessments.

Any paper documentation, which will be minimal for this study, will be held in access-controlled buildings within lockable rooms in lockable filing cabinets that only authorised personnel can access. All paper data transfers will be sent via recorded delivery or secure courier.

8.3 Access to data

Data will only be accessed and used by those who have permission. Access to data on network storage requires a valid Unit login (username and password). Access to data in the study's databases requires a password protected database account and access to PID is further limited to named users with additional 2-FA.

The data cannot be used or given to any other third party without documented permission of the participant, as explained in the participant information sheet.

Direct access will be granted to authorised representatives from the Sponsor, host institution and the regulatory authorities to permit study-related monitoring, audits and inspections, in line with participant consent.

Anonymised data sets may be shared with external collaborators for research purposes. Studies and analyses of the data collected will be subject to approval by the study investigators. Where external researchers wish to use participant-level data, we will require an agreement to be in place to cover data sharing and security. Where possible we will release data via in-reach to our servers, with a visiting worker agreement and appropriate data security training. Where data needs to be released externally then this will be covered by the study collaboration agreement (for SWIM investigators) or a formal Data Sharing Agreement

8.3.1 Data Protection/GDPR

The Data Protection Act defines "personal data" as any information relating to an identified or identifiable living individual. This is a living individual who can be identified, directly or indirectly, in particular by reference to (a) an identifier such as a name, an identification number, location

data or an online identifier, (b) or one or more factors specific to the physical, physiological, genetic, mental, economic, cultural or social identity of the individual.

This study is being conducted by the MRC Epidemiology Unit as part of the University of Cambridge and as such the legal basis to hold and use personal data is covered under the General Data Protection Regulation "Article 6(1) (e) processing is necessary for the performance of a task carried out in the public interest". To hold special categories of personal data our lawful basis is for pursuing scientific research under "Article 9(2) (j) processing is necessary for archiving purposes in the public interest, scientific or historical research purposes or statistical purposes in accordance with Article 89(1) based on Union or Member State law which shall be proportionate to the aim pursued, respect the essence of the right to data protection and provide for suitable and specific measures to safeguard the fundamental rights and the interests of the data subject".

8.4 Cauldron Science Ltd

The SWiM web-platform has been developed by Cauldron Science Ltd and is stored securely on Microsoft Azure which is a secure cloud-based web host. All data is stored in a Microsoft Azure SQL database; this is stored in two different data centres both located within the European Union. Data inputted into the SWiM web-platform, including name and email address are stored securely in the Azure SQL database, which is encrypted at rest and only accessible with both the correct credentials and a whitelisted IP address. The University of Cambridge and Cauldron Science Ltd hold a data confidentiality agreement. The web platform is stored in accordance with the University of Cambridge data standards and such data is only accessible to the study team and Cauldron as the technical providers. All content is the intellectual property of the University of Cambridge. The study team at MRC Epidemiology will be responsible for downloading the research data via a secure download directly from the SWiM platform.

8.5 Qualitative Interviews

The qualitative interviews and observations will be recorded on TEAMS, initially as a video/audio mp4 file. The CETU have a shared TEAMs channel configured so that it is only accessible to designated Research staff on that project. The recording will automatically save in the cloud on the University's Microsoft's 365 platform into SharePoint which the Researcher has access to using their RAVEN credentials. The video/audio mp4 file will then be converted into an audio only mp3 file using the software VLC once the file is on the SRD a separate server which requires two factor security authentications to access. Once safely transferred to the SRD, all files will be deleted from TEAMS. Recordings will be transcribed by an experienced external agency and checked for accuracy by the research team.

8.6 Data Storage and Archiving

Essential documents are defined as 'those which individually and collectively permit evaluation of the conduct of a trial and the quality of the data produced'. Essential documents are primarily held in the eTMF but also includes data held in study databases and source data.

Essential study documents, mostly in electronic form, will be archived in accordance with MRC policy for a minimum of 20 years after the study has ended. The process and monitoring will follow our CETU SOPs and department policies and will be described in detail in the Data Management Plan.

The Principal Investigators and Sponsor will take overall responsibility for data archiving with day-to-day responsibility delegated to the Database Manager and Study Coordinator. All data sets will be kept securely with no access from unauthorised personnel. Data will be stored so that it can be accessed, used and understood by subsequent users. When the investigators have completed their planned analyses, the anonymised data will be made available for use by others and will be shared under appropriate data sharing agreements. Primary data and the Trial Master File will be retained securely in their original form for a minimum of 10 years.

The MRC Epidemiology Unit will be responsible for archiving all documentation relating to the trial which will include consent forms, participant forms (screening questionnaires, CRFs, questionnaires), data, the study database, and results and associated files.

9. MONITORING AND ARCHIVING

9.1 Risk Assessment

A risk assessment will be written and approved by the CI before the first participant is invited. The risk assessment will help define all monitoring activities and frequencies.

9.2 **Monitoring**

A monitoring plan, approved by the CI, will describe the frequency and nature of monitoring activities, proportional to the risk identified in the Risk Assessment.

In accordance with the conditions and principles of GCP, an electronic Trial Master File (eTMF) will be established at the beginning of the study and held by the Study Coordinator at the MRC Epidemiology Unit. All essential documents, which together demonstrate the compliance of the study and study personnel with the conditions and principles of GCP and any applicable regulatory requirements, will be stored in the eTMF. The study risk assessment will determine the review frequency of the eTMF as per the CETU TMF Review SOP to confirm adherence to GCP guidelines and any applicable regulations.

Persons from regulatory bodies and representatives of the Unit and the sponsor may require access to participant level data to verify that the conduct of the study is in line with applicable regulations.

Those responsible for undertaking the collection of data from study participants will be subject to appropriate training, review and assessment by the relevant MRC Epidemiology Unit specialist before being deemed competent. Regular monitoring of the level and type of data queries will be performed by the Study Coordinator. This will inform any further training needs. In addition, the Unit's specialist teams will conduct quality control and assurance reviews, on at least an annual basis, in order to maintain a high level of competency and quality in the collection of data

10. SAFETY REPORTING

10.1 AE/SAE Definitions

An adverse event (AE) is any untoward occurrence in a participant that occurs as part of a test procedure whether related to that procedure or not. Test procedures include direct measurements, be they at a testing site or in a free-living environment. For example, a participant who faints whilst having a blood sample taken is experiencing an AE. Monitoring these events enables us to improve our test procedures and responses to future events.

A Serious Adverse Event (SAE) is any untoward medical occurrence or event that either:

- Results in death or is life-threatening
- Requires hospitalisation or prolongation of existing hospitalisation
- Results in persistent or significant disability or incapacity
- Consists of a congenital anomaly or birth defect
- Is otherwise considered medically significant by the investigator

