2.2 Objectives

Clinical Effectiveness

Primary Objective:

To evaluate the effect of SWiM versus standard care on weight at 12 months

Secondary Objectives:

- To evaluate the effect of SWiM versus standard care on weight at 6 and 24 months
- To evaluate the effect of SWiM versus standard care on body composition, glycated haemoglobin (HbA1c), psychological well-being, and psychosocial outcomes at 6, 12, and 24 months.
- To evaluate whether the effectiveness of SWiM is moderated by demographic characteristics (PROGRSS-Plus criteria)²⁵ of participants or the weight loss intervention used to lose weight or amount of weight lost before joining the trial.

Process Evaluation Objectives

- To examine how the programme works (i.e., mechanisms of action).
- To explore how SWiM is perceived, experienced, and applied over time across individual contexts.
- To explore why components of SWiM work or do not work, and under what contexts.
- To explore what additional unintended outcomes (positive/negative) are experienced.
- To examine the extent to which SWiM is delivered as intended.
- To understand the contextual factors influencing the delivery of SWiM, by exploring health coaches' perceptions and experiences of delivering SWiM, including barriers and facilitators to delivery.

The NICE NG246 guideline calls for more research on weight management interventions in ethnic minority groups. This study will aim to address this gap by exploring differences in intervention effects across demographic groups.

Cost-Effectiveness Objectives

- To estimate the effect of SWiM versus standard care on health care utilisation, out of pocket spend on weight management services, and work productivity at 6, 12 and 24 months.
- To model the long-term cost-effectiveness of SWiM and its impact on health outcomes and related health care costs
- To evaluate whether the long-term cost-effectiveness of SWiM is different depending on initial weight loss or weight loss programme.
- To evaluate whether the long-term cost-effectiveness of SWiM differs by demographic characteristics.

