10.2 Recording and reporting AEs and SAEs

The Sponsor expects that adverse events are recorded from the point of Informed Consent. Given the remote nature of this study, we do not expect there to be a large number of adverse events.

There are no expected SAEs for this study.

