10.3 Reporting Responsibilities

Adverse events experienced by study participants will be recorded, followed-up and reviewed by an investigator as per the CETU SOP for recording and reporting adverse events. The Operational Group will monitor the frequency and type of adverse events during each of their scheduled meetings. In addition, the monthly CETU Steering Group Meeting will receive a report on the numbers of adverse events recorded during the previous month.

All Serious Adverse Events will be reported to the Chief Investigator using the CETU SAE form within 24 hours of awareness of the event. The Chief Investigator is responsible for ensuring the assessment of all SAEs for expectedness and relatedness is completed and the onward notification of all SAEs to the Sponsor if applicable as per CETU SOP for recording and reporting adverse events.

Serious Adverse Events (SAEs) that are related to the study (i.e. those that result from administration of any of the research procedures) and are unexpected (i.e. not listed in the protocol as an expected occurrence) will be emailed to the REC using the Non-CTIMP safety report to REC form. These will be sent within 15 days of the chief investigator becoming aware of the event. There is no requirement for annual safety reports in addition to the information provided through the annual progress report.

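### The adverse event definition in section 10.1 covers only test procedures, so non-serious harms of SWiM outside a measurement are not adverse events and cannot be compared by arm from adverse event data

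*Protocol*

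**What the plan says.** Protocol section 10.1 defines an AE as "any untoward occurrence in a participant that occurs as part of a test procedure whether related to that procedure or not". It continues: "Test procedures include direct measurements, be they at a testing site or in a free-living environment". Its example is a participant who faints while blood is being taken, and its stated purpose is that "Monitoring these events enables us to improve our test procedures and responses to future events".

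The SAE definition in the same section has a different scope. It begins "A Serious Adverse Event (SAE) is any untoward medical occurrence or event that either", lists the seriousness criteria and ends with a catch-all: "Is otherwise considered medically significant by the investigator". It does not mention test procedures.

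Section 10.2 sets the start of recording: "The Sponsor expects that adverse events are recorded from the point of Informed Consent". Section 10.3 has AEs recorded and reviewed under a unit SOP, and their numbers monitored by the Operational Group and the unit's steering group. For SAEs that go to the ethics committee, it explains relatedness to the study as "i.e. those that result from administration of any of the research procedures".

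Among the process evaluation objectives, section 2.2 includes "To explore what additional unintended outcomes (positive/negative) are experienced". Section 6.3 assigns that question to the qualitative interviews.

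**The concern.** SWiM is a psychological intervention. Its sessions (section 4.1, Table 3) deal with emotional eating, cravings, weight stigma and body image, and participants are encouraged to weigh themselves weekly. The harms one would want to know about are mostly non-serious and would arise between assessments: distress provoked by a session, for example, or a minor injury after becoming more active. The AE definition is built around the measurement procedures, which are the same in both arms, and not around the intervention, which is what differs between them.

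If the definition is followed as written, the AE count describes finger-prick tests and weighing. The groups that monitor AE numbers would see mainly those events, and section 14 provides no separate data monitoring committee. A low AE count at the end of the trial would then say little about whether SWiM is well tolerated, although a reader of the results would probably take it that way.

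**Working it through.** The point is one of definition. The protocol gives no AE rate or other harms figure to reproduce, so the check is to set the relevant passages side by side.

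**1. Does the 10.1 definition reach the intervention?** The defining clause requires the event to occur as part of a test procedure. The words that relax the causal link (whether related or not) apply only to events that have already met this condition. The gloss names measurements, the example is a blood sample, and the purpose is better test procedures. The verb *include* leaves the gloss open in principle, but nothing in 10.1 mentions sessions, the web platform or coach calls. A slip while stepping on the study scales would count. Distress after a session would not.

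**2. Do later sections widen it?** Section 10.2 fixes when recording starts, not what is recorded. Section 10.3 says what is done with AEs. Both use the term that 10.1 defines, and neither redefines it.

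**3. Is 10.1 consistent with itself?** No. An SAE needs only to be an untoward medical occurrence that meets a seriousness criterion. A hospital admission unconnected with any measurement is therefore an SAE but not an AE, although SAEs would ordinarily be a subset of AEs.

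**4. What can be compared by arm now?**

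| Type of harm | Source | Comparable by arm? |
|---|---|---|
| Serious events | SAE definition, 10.1 | Yes, no test-procedure limit |
| Worsening of depression, anxiety, binge eating, wellbeing | Table 2; 3.5.2; 5.2 | Yes, secondary outcomes at 6, 12 and 24 months, analysed in a similar way to the primary outcome |
| Health outcomes and health care use | Section 3.3.3 and Table 2, self-report | In part; nothing links them to AE recording |
| Non-serious events during a measurement | AE definition, 10.1 | Yes |
| Non-serious events outside a measurement | None as AEs | Not from AE data |

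The last row is the gap. The scales narrow it but do not close it, because a mean change in score does not record a discrete event.

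**5. Do the interviews fill the gap?** Section 6.3 plans purposive interviews with an estimated 15 participants and states no between-arm comparison. They can describe kinds of harm, but they are not meant to estimate or compare frequencies.

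**6. What happens if only the wording is widened?** Section 4.1 gives SWiM participants 4 scheduled calls, 3 optional calls and up to 3 re-engagement calls, at most 4 + 3 + 3 = 10. Section 4.2 gives controls no additional structured support. Table 2 lists no AE question. Spontaneous reports under a wider definition would therefore come mainly through the coaches, that is, from one arm. A wider definition thus needs a common method of elicitation.

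**The case against.** The best defence is that the protocol already collects much of what matters. SAEs are unrestricted and carry a medical-significance catch-all. Depression, anxiety, stress, binge eating and wellbeing are measured in everyone, so the harms most plausible for this intervention are covered at least on average. The trial is described as low risk and is run remotely. The unit SOP cited in 10.3 is not shown and may define or elicit AEs more broadly. Most of this stands and limits the point, but it does not remove it. If the SOP is broader, it conflicts with the protocol's own definition and the two must be reconciled.

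Some stronger readings are tempting but are not supported:

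- A reader might infer that the trial cannot compare harms by arm at all. It can, for SAEs and for the scheduled scales.
- A reader might infer that 10.3 excludes SWiM from relatedness. It speaks of research procedures, not test procedures, and does not clearly leave out the randomised intervention. Naming SWiM is a clarification.
- A reader might infer that coach contact already tilts non-serious AE counts towards SWiM. Under the present definition only events during measurements count, and the measurement schedule is common to both arms. The imbalance becomes a problem for these events only once the definition is widened.
- A reader might try to bound the harm rate from an absence of harms in the interviews. The sample is purposive and not designed to estimate a rate, so such a bound would mean little.
- The lack of a by-arm AE table in the protocol is no defect, since the statistical analysis plan may provide one.

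**Conclusion.** The point holds in a limited form. As written, section 10.1 leaves non-serious harms of SWiM that occur outside a measurement out of the AE definition, so AE data cannot compare them by arm. It is also inconsistent with the SAE definition beside it. SAEs and the scheduled self-report measures can still be compared.

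No numerical size can be given, because the documents state no expected frequency of such events. The primary outcome, its analysis and the sample size are untouched; what is affected is the statement on harms that the trial can make. The conclusion assumes that *test procedure* carries the measurement meaning that its gloss, example and purpose give it, and that the protocol's definition governs what is recorded. The change is worth making because it is cheap and the loss cannot be recovered after follow-up.

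**What to change.** Three changes, in one amendment:

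1. In section 10.1, define an AE as an untoward occurrence in a participant from consent to the end of follow-up, whether or not linked to a measurement or to SWiM. This makes SAEs a subset of AEs. Check the unit SOP against the new wording.
2. In section 10.3, state that research procedures include the SWiM intervention.
3. Add one AE item, worded identically for both arms, to the existing 6-, 12- and 24-month questionnaires, and use it as the common source for comparing arms. Events that coaches hear of would still be recorded, but identified as coming from that route.

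The cost is the amendment wording, one further questionnaire item and more minor events to log and review.
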